### *Study Size*

In order to determine the study size, we looked at 114 consecutive epidural placements as part of our routine quality assurance with the Arrow® Epidural Catheterization Kit at Von Voigtlander. We found that in 11% (n=12) of epidurals placed, the epidural catheter did not thread on the first attempt. In a separate quality assurance check we retrospectively reviewed 100 epidural placements finding out that in 1% (n=1) of epidurals placed, the epidural catheter did not thread on the first attempt. A sample-size analysis for the primary outcome shows that 107 epidural placements per group would provide a power of 80% to detect a difference in proportion between the two techniques of 0.10 at the 0.05 level. Considering an attrition of 10-20% for follow-up and data missing, a total number of 240 epidural placements will be collected. Power calculations were computed using PASS 14.

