#### *Monitoring and Quality Assurance*

The accuracy and completeness of all documents will be monitored on an on-going, weekly basis by the principal and co-investigator. All data will be collected at the time of each epidural placement, analyzed for completeness, and filed. The principal investigator and co-investigators will follow the validity and integrity of the data and adherence to the IRB approved protocol.

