## Ease of Threading the Epidural Catheter

- |   |                              |
|---|------------------------------|
|  Easy thread without further maneuvers  |                              |
|  hydrodissection, then catheter:  | Thread Did not thread |
|  new catheter from the same brand, then catheter:   | Thread Did not thread |
|  Rotated the needle, then catheter:   | Thread Did not thread |
|  Changed needle angle, then catheter:   | Thread Did not thread |
|  Withdrawal and re-advanced the needle with an additional LOR (this count as an additional attempt), then catheter: | Thread Did not thread |
|  Advanced the needle blindly, then catheter:  | Thread Did not thread |
|  Changed space  |                              |

Patient Comfort at 30 minutes (VAS  $\leq$  10/100) YES NO

Additional Number of attempts after loss of resistance 0 1 2 3 4 5

Complications (circle all that applies)

Wet tap Paresthesias Intravascular Other (please explain)

Epidural analgesia failed and then epidural Replaced? YES NO

Delivery date \_\_\_ and Time \_\_\_\_\_

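### The complications item has no negative answer, so a blank cannot be told from no event; separately, the rule that all data are collected at placement conflicts with form fields known only later

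*Combined protocol and SAP*

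**What the plan says.** The study form (Ease of Threading the Epidural Catheter) records complications under "Complications (circle all that applies", and the choices are "Wet tap Paresthesias Intravascular Other (please explain". No choice stands for no complication. Other outcome items on the same form do allow an explicit negative: comfort at 30 minutes is YES or NO, additional attempts run from 0 to 5, and replacement reads "Epidural analgesia failed and then epidural Replaced? YES NO".

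Objectives and Statistical Analysis name unintended dural puncture, paresthesia and intravascular cannulation as secondary outcomes, each to be compared by chi-square or Fisher's exact test. Table 2 has a row for each, and one for replaced epidurals.

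On timing, Monitoring and Quality Assurance states: "All data will be collected at the time of each epidural placement, analyzed for completeness, and filed". The same section says "The accuracy and completeness of all documents will be monitored on an on-going, weekly basis". The form nevertheless contains "Patient Comfort at 30 minutes", the replacement item and "Delivery date" with a time.

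The documents do not say how a blank complications item is coded, or who completes the later fields and when.

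**The concern.** There are two separate problems.

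The first is ambiguity in the complications item. If the provider circles nothing, the analyst cannot know whether nothing happened or the item was passed over. Counting every blank as event-free keeps unanswered items in the denominator and can pull the recorded rates down. If item completion differed between kits, it could also create or hide a difference. These are the study's safety comparisons between kits, and Objectives says the findings are meant to guide which kit the hospital uses. The form alone cannot resolve the ambiguity afterwards.

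The second is the timing rule. Followed literally, it closes the form before three of its fields can be known. A blank in one of those fields would show. A NO for replacement circled at placement would look complete but would not be an observed outcome.

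**Working it through.** **Can a skipped item be seen?** Set the form fields side by side.

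| Field | Explicit negative? | Blank visible as missing? | Known at placement? |
|---|---|---|---|
| Complications (circle list) | No | No | Mostly |
| Comfort at 30 minutes | Yes (YES/NO) | Yes | No |
| Additional attempts | Yes (0 to 5) | Yes | Yes |
| Replacement | Yes (YES/NO) | Yes | No |
| Delivery date and time | Not applicable | Yes | No |

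Only the complications item fails the third column. The form's dural puncture epidural questions concern deliberate use of that technique and do not substitute for the wet tap entry. Three fields fail the last column, and these are where the form and the monitoring section conflict.

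**Inputs.** The documents give 120 placements per kit (Randomization Procedure) and the choice of chi-square or Fisher's exact test (Statistical Analysis). They give no complication rate and no item-omission rate, so every rate below is an assumption. The one sample-size figure, 107 per group, concerns threading failure. It reproduces from 0.11 v 0.01 (two-sided 0.05, 80% power, continuity-corrected) and has no bearing on this point.

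**Bias if blanks are read as none.** Suppose a share m of items is left blank independently of whether an event occurred. Then recorded rate = true rate × (1 − m).

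| Assumed true rate | m = 5% | m = 10% | m = 20% |
|---|---|---|---|
| 1% | 0.95% | 0.9% | 0.8% |
| 5% | 4.75% | 4.5% | 4.0% |
| 10% | 9.5% | 9.0% | 8.0% |

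At a true 5%, the expected 120 × 0.05 = 6.0 events per kit become 5.7, 5.4 or 4.8. If items are left blank only when nothing happened, no event is lost and the bias is zero.

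**Unequal blanks.** Assume a true 20% in both kits, with 5% of items blank in one and 20% in the other. The recorded rates are 0.20 × 0.95 = 19% and 0.20 × 0.80 = 16%. By exact enumeration at 120 per kit, Fisher's test rejects at 0.05 in 6.6% of trials, against 3.4% with no blanks.

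**Power.** Assume a true 20% v 8%, two-sided 0.05, exact enumeration of Fisher's test:

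- No blanks, 120 per kit: 0.718.
- 20% blank, read as none: rates become 16% v 6.4% at 120 per kit, power 0.587.
- 20% blank, treated as missing: rates stay at 20% v 8% with 120 × 0.80 = 96 per kit, power 0.612.

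The total loss is 0.718 − 0.587 = 0.131. Coding blanks as missing recovers 0.612 − 0.587 = 0.025. Most of the loss comes from the absent information, and only fewer blanks, or blanks that are queried and filled, would recover it.

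**The case against.** The strongest reply is that a provider faced with a circle list most naturally leaves it blank when there is nothing to report, in which case reading a blank as none is correct. That stands as a reason to say the rates may be biased, not that they are. It does not make the item checkable.

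A reader might infer that replacement suffers the same defect. It does not: the item is YES/NO, so a blank is visible, as it is for comfort and delivery time. The remaining risk is a NO entered early and never corrected, and nothing in the documents says staff would do that.

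A reader might also infer from the monitoring section that forms really are filed before replacement can be known. The delivery field suggests otherwise, and Minimizing the Risk for Subjects also refers to delivery as the end point for identifiable data. The texts conflict; actual practice is not shown.

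It is tempting to take "Considering an attrition of 10-20% for follow-up and data missing" as the share of blank complications items. That figure is a general allowance in the sample-size calculation, not an item-level rate. A wholly lost record would leave both numerator and denominator and would not be read as event-free.

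There are partial safeguards. A skipped section would show in the neighbouring items, so only an isolated skip is hidden. The Data and Safety Monitoring Plan has source data reviewed at about 120 placements, which might catch some omissions if the source includes more than this form. Dural puncture, paresthesia and intravascular placement are mostly evident at or soon after insertion, so the timing conflict matters little for them.

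**Conclusion.** The point holds in a limited form. The complications item cannot distinguish none from not recorded, and no completeness check on the form can repair that for three tested secondary outcomes. The rule on timing of collection contradicts the form and has to be reconciled with it.

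Bias towards zero is possible, not demonstrated. It requires blanks to be counted as event-free and some blanks to hide events. Differential bias between kits further requires unequal omission; open-label weekly allocation makes that conceivable, but nothing in the documents shows it. Even a fourfold imbalance in blanks moves the rejection rate only from 3.4% to 6.6% under the assumed 20% rate. All sizes rest on assumed rates and, for the formula, on blanks that are independent of events.

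The primary threading outcome and the sample size are unaffected. Severity is minor; the change is worth making because it costs almost nothing.

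**What to change.** On the form, replace the circle list with YES/NO for wet tap, paresthesia and intravascular cannulation, keeping the free-text entry for other events; alternatively, add a None choice. State in Statistical Analysis that an unanswered item is missing, is queried while it can still be answered, and is not counted as event-free. Report the number answered for each item.

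In Monitoring and Quality Assurance, replace the single collection time with three: placement items at placement, comfort at 30 minutes, and replacement and delivery time at delivery. Name the role that completes the later fields, and run the completeness check once they are filled.

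The cost is a form edit and a few sentences of text, with no added procedure or visit. The only downside is slightly smaller reported denominators where items remain unanswered.
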